(additional breast cancer centers in Norway may be involved if patient recruitment is not reaching the expected pace);

Patients:

Patients diagnosed with (biopsy-confirmed) locally advanced (defined as either large T2, or T3/T4, or N2-3), ER-positive (≥50% pos. cancer cells), HER-2 negative, luminal-A/B breast cancer suitable for neoadjuvant antihormone therapy will be considered for this protocol; At least 100 patients should complete all study procedures. Thereafter, the protocol will be closed for further inclusion, but each patient included up to that time will be completed according to the protocol. The patients will be followed by the involved medical oncologists for up to 10 years after surgery or until relapse (whatever comes first).

Statistical considerations:

Based on the results of the CORALLEEN trial ¹ investigating neoadjuvant ribociclib treatment of luminal B patients, the spread between level of treatment response (24 weeks of treatment) based on MRI was 14% Complete Response (CR), 43% Partial Response (PR), 33% Stable Disease (SD) and 10% N/A. We propose a minimum sample size in either group to be at least >30 patients, thus an inclusion goal of 100 patients in total would be sufficient for hypothesis generating results. However, it is important to mention that the purpose of this trial is to deliver basic research results and not primarily to evaluate the efficacy or comparisons of treatments. Based on the major endpoints and their anticipated data variation, the data will be sufficient to come to reliable results. Finally, statistical power is added as all patients will serve as their own controls based on sequential intra-patient data obtained over time (in general 180 days all in all).

This is aligned with advice given by gastroenterologists and on par with earlier studies that allowed for characterization of the tumor immune microenvironment and the gut microbiota ^{2,3} and gives sufficient statistical power to prioritize biomarkers for larger companion diagnostic studies in the future.

Treatment:

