increase the antigen presentation of cancer cells, to increase the activity of tumor infiltration by CD45+ cells and effector T cell activation, as well as to decrease the Treg cell proliferation ^{42,44,45}. While these mechanisms have been well described in *in vitro* and animal models, they have to be studied in humans as soon as possible to understand them and to allow to take advantage of these novel aspects in clinical decision making. In addition, an immunomodulatory effect of e.g. CDK4/6 inhibitors warrants further investigation and confirmation to allow for optimal drug combinations and enable concomitant anti-tumorigenic effects of drugs. These findings may also pave the way for microbiome and immune-related data as potential biomarkers for patient selection and response evaluations during therapy in the long run.

In addition to the clinical effects as standard care for breast cancer patients suffering from locally advanced breast cancer, neoadjuvant therapy is widely used to study the endocrinology of breast cancer in general ⁴⁶ and is recognized as one of the best model systems to predict responses in other clinical settings (early breast cancer or metastatic breast cancer) as well ⁴⁷.

Tumor biopsies obtained before initiation of treatment and following six months on therapy will allow correlations to the individual type of clinical response (partial responses vs complete responses etc.). We will focus on intratumor mechanisms of adaption through tumor characterization using single cell technology which will allow us to follow both (i) the different cancer clones but also (ii) the evolution of different immune cells during therapy. We will use novel approaches to evaluate liquid biopsies (measurement of cytokines levels, metabolites and cell free DNA-fragments etc.) during letrozole and ribociclib using state of the art laboratory methods at our hospital and in the laboratories

of our listed collaborators. Finally, basic information on intra-tumor gene expression and regulation in individual breast cancer patients treated with both drugs in concert will become available in the planned spin-off-studies involving some of the leading cancer research teams in the world.

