All cancer drugs used in this trial (letrozole, ribociclib, goserelin) are well-established in MBC and have also proven high efficacy in previous neoadjuvant trials in locally advanced breast cancer, both as monotherapy and in combination ^{4,49-58}. Thus, it is known that most of the patients will have clinical benefit from these medications and many will be able to avoid neoadjuvant/adjuvant chemotherapy that is associated with considerable more serious side-effects compared to study medication. However, if patients do not profit sufficiently from the medication given in this trial, they will be taken off study medication and be treated with all available types of standard chemotherapy established for these patients (no restrictions caused by the present protocol). In addition, all patients will be considered for adjuvant therapy according to the final pathological report following surgery (yTNM-status) and according to the Norwegian breast cancer guidelines published by the Norwegian Breast Cancer Group (www.nbcg.net).

MEDICAL EVALUATIONS and SAMPLING

Clinical evaluations

In general, patients will be followed at the outpatient clinics (Akershus University Hospital, Department of Oncology & Drammen Hospital, Department of Oncology) by experienced medical breast cancer oncologists at least every 4 weeks during the entire study (including caliper measurements of maximum tumor diameters). In addition, measurement of maximum tumor diameters will be performed at study entry and during therapy every 3 months by advanced MRI (ax T1, T2, DWI, dynamic study and spectroscopy) and Spectral-CT scans at

the Departments of Radiology, Akershus University Hospital and Drammen Hospital. All measurements (MRI, spectral-CT etc.) will be performed always prior to biopsies at baseline and before final surgery as usual to avoid that bleeding etc. may interfere with the diagnostic procedures. Patients will be informed about the opportunity to perform PET-scanning prior to treatment after protocol as a general screening procedure for distant metastasis (not mandatory). All patients will be screened for distant metastasis by CT-scanning (thoracic, abdominal and pelvic CT-scanning as well as a bone-scintigraphy) at study entry. All available additional diagnostic procedures may be used at the discretion of the responsible oncologists / breast cancer surgeons (not mandatory).

Blood samples (scientific samples)

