at Ullevål University Hospital at the same time as the scRNA-seq. Neoantigen detection will be performed by collaborators at Karolinska Institute, Stockholm University, Sweden ([name] laboratory) using state of the art proteomics quantification and analysis ⁵⁹.

Based on recent results we will also evaluate whether responders *vs* non responders of this drug combination (AI + CDK4/6i) belong to a newly discovered immune-related breast cancer subtype ³⁰. Subtyping for these *immune-clusters* will be performed by the inventor of the method.

2. Study the mechanisms of adaptation and resistance to aromatase inhibitor (letrozole) in combination with the CDK4/6-inhibitor ribociclib.

We will use the samples collected at diagnosis and after treatment (at surgery) to follow the changes in tumor and immune cell phenotypes. We will profile each cell of the tumor tissue using single-cell RNA-seq (scRNA-seq). This method allows us to profile thousands of individual cells and to build complex cellular atlases of whole tumors biomarkers for targeted cancer treatments ⁶⁰. scRNA-seq will allow us to characterize which exact cancer cell phenotypes (clones) are eradicated by the treatment combination and find biomarkers of response while monitoring which cancer cells survive or are expanding under the treatment pressure. Being able to find the cancer cells surviving treatment will allow to pave the way to designing the next treatment options for the patients not responding to the here propose treatment regimen. We have established the scRNA-seq method on primary breast tumors (Figure 2), these data are the first scRNA-seq data performed on solid tumors in Norway.

The experimentation will be conducted at Ullevål University Hospital using the 10X GENOMICS platform for single cell analysis.

Figure 2: scRNA-seq of primary breast tumor (preliminary results).

A: tSNE clustering of ~ 5.000 cells from breast tumor. A dot represents a cell, A color, a cell type, we therefore identify several cell phenotypes in this breast tumor.

B: On the respective t-SNE plot the expression of CD8 a marker of cytotoxic immune cells is plotted showing that the cells on the top left are T lymphocytes.

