Detection of circulating free tumor DNA (cftDNA) during follow-up after initial treatment for early breast cancer was associated with a high risk of relapse ⁶⁷. This gives the rationale to collect blood samples after surgery and end of treatment as it has strong potential to early detect the patients relapsing and or at risk of relapsing. Circulating free DNA will be extracted and sequenced at Akershus University Hospital.

RECRUITMENT TIME

Starting on December 1st. 2020 (or when the protocol is approved by local authorities and at the hospital level) until all patients are recruited (estimated recruitment period: 2 years).

SUBSEQUENT THERAPY

All patients treated following this protocol will be evaluated by an experienced breast surgeon for the best local surgical treatment option (breast conserving surgery or mastectomy including necessary procedures including the ipsilateral axilla).

After surgery, all patients will be considered for adjuvant treatment (both endocrine options and chemotherapy but also zoledronic acid etc.) according to

the national recommendations (Norwegian Breast Cancer Group; www.nbcg.net).

Patients with progressive diseases (at any time point) during neoadjuvant therapy or stable diseases following 3 months of therapy according to this protocol, will be able to obtain additional therapies (chemotherapy etc.) without any restrictions to allow down-staging prior to surgery by other means.

PROTOCOL AMENDMENTS AND SAE REPORTING

If necessary, protocol amendments will be done in collaboration with all involved parties and the regional ethical committee will be informed about all changes prior to implementation.

ADVERSE EVENT (AE) REPORTING

AE definition

An adverse event (AE) is defined as the appearance (or worsening in the case of pre-existing conditions) of any undesirable sign, symptom or disease that arises after having obtained the patient's informed consent, regardless of if it is considered to be related to the study drug. Any abnormal analytical values or test results occurring after obtaining informed consent shall only be reported in the eCRF under adverse events when there are clinical signs or symptoms, they are considered clinically relevant, they require treatment (for example, a hematological abnormality that requires transfusions or supportive therapy with hematopoietic stem cells) or require the study medication to be modified.

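### Does the sample-size paragraph fail because it asks for more than 30 patients per group without naming the groups?

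*Combined protocol and SAP*

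**What the plan says.** The combined protocol and SAP justifies its size in SHORT SUMMARY, Statistical considerations. It cites an MRI response split at 24 weeks from a trial in luminal B patients, "14% Complete Response (CR), 43% Partial Response (PR), 33% Stable Disease (SD) and 10% N/A", and continues: "We propose a minimum sample size in either group to be at least >30 patients, thus an inclusion goal of 100 patients in total". The same paragraph calls the results hypothesis generating, says that comparing treatments is not the main purpose, and relies on patients as their own controls. It then adds that the size "gives sufficient statistical power to prioritize biomarkers for larger companion diagnostic studies in the future".

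SHORT SUMMARY, Patients, sets the closing rule: "At least 100 patients should complete all study procedures". Inclusion closes only after that, and everyone already included is still taken through the protocol. PATIENTS AND TREATMENT, Patients, repeats the rule and aims for equal numbers of luminal A and luminal B.

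Response groups appear in two other places. BACKGROUND AND AIMS OF THE STUDY says that biopsies will "allow correlations to the individual type of clinical response (partial responses vs complete responses etc".) Study endpoints, item 1, asks whether responders as against "non responders of this drug combination (AI + CDK4/6i) belong to a newly discovered immune-related breast cancer subtype".

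**The concern.** A four-category split is followed by a minimum for each of an unspecified pair of groups, and 100 is presented as the consequence. The step cannot be audited without knowing which groups are meant. If complete response is one of them, 14% of 100 is less than half the stated minimum.

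Even for responders versus non-responders, 33 is only just above 30, so chance could take the smaller group below it. Three further features point the same way:

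- The denominator is an inclusion goal in one sentence and a completer count in another.
- Non-responders are the patients most likely to leave a completer count. Under Treatment, "if patients do not profit sufficiently from the medication given in this trial, they will be taken off study medication", and under SUBSEQUENT THERAPY patients with progression or "stable diseases following 3 months of therapy according to this protocol, will be able to obtain additional therapies".
- The cited rates come from postmenopausal luminal B patients, while this trial also admits luminal A and premenopausal patients.

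The sentence on power for biomarkers comes with no effect size, error rate or multiplicity rule, although one assay alone is a 54-plex cytokine panel. At stake is whether response-related biomarker findings would be read as resting on adequately sized groups.

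**Working it through.** **Inputs.** Complete response 14%, partial response 43%, stable disease 33%, not available 10%, minimum above 30 (at least 31) and 100 patients are from SHORT SUMMARY. Completion rates, overshoot, 80% power and two-sided 5% are assumptions; the documents give none.

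**The plan's own figure.** The shares sum to 14 + 43 + 33 + 10 = 100. Responders: 14 + 43 = 57 per 100. Non-responders: 33, or 33 + 10 = 43 if patients without a category count as non-response. Both groups exceed 30. The smallest total with 31 expected at 33% is 31/0.33 = 93.9, so 94, and 100 covers it. Luminal A versus B at 1:1 needs 2 × 31 = 62. Complete responders alone: 14 expected, and P(Bin(100, 0.14) > 30) = 0.00001.

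**Chance that both response groups exceed 30 at exactly 100** (exact binomial or multinomial):

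- 100 included, uncategorised patients lost (57/33/10): 0.70
- 100 included, uncategorised counted as non-response (57/43): 0.995
- 100 completers, completion unrelated to response (0.57/0.90 = 63.3%, 0.33/0.90 = 36.7%): 0.90

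**Effect of the closure rule.** At least 100 must complete, and patients then on treatment also continue. If about 100 patients enter evenly over the estimated 2 years (100/24 ≈ 4 per month) and treatment lasts 6 months, about 25 are in progress when the 100th completes. That overshoot is assumed, but its direction follows from the text. If a fraction c of stable-disease patients complete and all responders do, the non-responder share is 0.33c/(0.57 + 0.33c).

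| Completers | c = 1 | c = 0.9 | c = 0.8 | c = 0.7 |
|---|---|---|---|---|
| 100 | 0.90 | 0.78 | 0.59 | 0.35 |
| 110 | 0.976 | 0.93 | 0.81 | 0.60 |
| 125 | 0.998 | 0.99 | 0.96 | 0.86 |

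**A different response rate.** For an assumed non-responder share of 30%, the chance is 0.45 at 100 and 0.92 at 125. For 25% it is 0.10 and 0.56. For 20% it is 0.006 and 0.11.

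**Cost of falling below 30.** The normal-approximation detectable difference for one test is (1.96 + 0.84) × √(1/n₁ + 1/n₂) standard deviations:

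- 63 versus 37: 2.80 × 0.207 = 0.58
- 70 versus 30: 2.80 × 0.218 = 0.61
- 75 versus 25: 2.80 × 0.231 = 0.65

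Thirty is therefore not a cliff. Missing it by five patients moves the detectable difference by about 0.04 SD.

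**The case for a change.** The strongest case for acting is that naming the groups, the denominator and the handling of uncategorised patients costs only words, and that doing so before results are seen prevents groupings being chosen afterwards. The plan itself asserts statistical power, so calling the results hypothesis generating does not excuse an absent calculation. Using patients as their own controls helps within-patient change, not contrasts between response groups.

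Much of this is factually right. The groups are unnamed, the 10% have no stated rule, and the power sentence has no calculation behind it. Selective loss of non-responders is plausible, and a response rate well above the cited one would leave fewer than 31 of them even with overshoot.

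Two parts do not stand. The failure for complete responders answers a claim the plan does not make: the sample-size paragraph does not name them as a group, and the mention of partial versus complete response is background. The same goes for response comparisons within one luminal subtype. Two groups of 31 cannot fit in about 50 patients, but no such comparison is planned. Also, a demand that both groups exceed 30 with high probability is an outside standard. The plan sets a planning minimum and promises no level of assurance.

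**Conclusion.** No change is needed. On the natural reading, responders versus non-responders, the stated minimum is met in expectation at the cited rates (57 versus 33 per 100 included, about 63 versus 37 per 100 completers), and no figure in the paragraph is wrong. The chance of both groups exceeding 30 is 0.70 on the least favourable reading of 100 at those rates, with completion unrelated to response. On the completer rule it is 0.90, rising to 0.998 at 125 completers. These values rest on the cited luminal B rates carrying over and, for the last two, on completion being unrelated to response. The lower values in the working come from assumed completion or response rates.

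What remains is missing detail of a kind analysts fill when they report: they state who counts as a responder, give the observed group sizes, and present a small complete-responder group descriptively. Rewording would not alter enrolment or the number of non-responders. The power sentence is loosely put, but it concerns choosing candidates for later studies, and no confirmatory test depends on it. The primary endpoint, change in the tumour's immune profile within each patient, does not use these groups.

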All in all, tumor tissue samples (each about 500-1000 mg of tumor tissue) will be obtained at three time points (at baseline, after 21 days on treatment and after 6 months of treatment) and either stored or processed immediately for scRNA-seq. The tumor tissue will be divided in four portions as described below. One sample (ca. 250-500 mg) will be stored immediately in liquid nitrogen (transport medium to the research departments and will be primarily used for RNA and DNA extraction) before the sample is stored at -80°C until processing otherwise. The second sample (ca. 250-500 mg) will be immediately (within 24h) dissociated at the single cell level for single cell RNA profiling and single cell Tcell receptor sequencing. The third tissue sample will be prepared for histology assessments at the departments of pathology, (ca. 100-300 mg, stored in formalin before it will be paraffin-embedded as usual). A fourth sample will be stored in RNA-later over night at 4°C and then transferred to -80°C. The tissue samples will be prepared as quickly as possible (max. time: 5-10 minutes) preferably in the operational theatre, trimmed (if necessary) for fat and blood as usual. In general, all biopsies will be obtained as either open (surgical) biopsies or ultrasound guided biopsies using adequate local anesthesia. Vacuum-biopsies are also allowed. During final surgery, the scientific tumor biopsy will also be obtained through the skin whenever possible to avoid manipulation of the posterior surface of the breast (allowing the normal evaluation of free margins, distance to tumor tissue etc.). If patients need additional neoadjuvant treatment following 6 months of therapy according to this protocol, the biopsy scheduled after 6 months is giving critical information and should therefore be obtained for all patients.

Pathology / Histology

As described above, a baseline tissue biopsy will be used to ensure that the right patients are selected for the protocol and will provide all routinely needed standard information such as subtype of breast cancer, grading, ER-status, PGR-status, HER-2 status and level of Ki67-expression. For this purpose, a formalinembedded sample will be prepared as usual at baseline and at all subsequent time points. All following (scientific / non-diagnostic) biopsies will be investigated by a pathologist to ensure that the biopsy is consisting of tumor tissue.

Fecal samples

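### Do the tumour-tissue portions exceed the biopsy they are cut from, so that a small biopsy leaves nothing for histology?

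*Combined protocol and SAP*

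**What the plan says.** All the masses stand in one paragraph of the protocol, under Tissue samples. It gives the yield at each visit ("tumor tissue samples (each about 500-1000 mg of tumor tissue) will be obtained at three time points") and then the split: "The tumor tissue will be divided in four portions as described below".

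- Portion 1: "One sample (ca. 250-500 mg) will be stored immediately in liquid nitrogen". It is mainly for RNA and DNA extraction.
- Portion 2: "The second sample (ca. 250-500 mg) will be immediately (within 24h) dissociated at the single cell level". It is for single-cell RNA and T-cell receptor sequencing.
- Portion 3: histology, "ca. 100-300 mg, stored in formalin before it will be paraffin-embedded as usual".
- Portion 4: "A fourth sample will be stored in RNA-later over night at 4°C and then transferred to -80°C". No mass is given.

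No order of priority is stated for a small biopsy. The following section, Pathology / Histology, commits the trial to a formalin-embedded sample at baseline and at every later time point, and to a pathologist's check that each later biopsy contains tumour. The summary and the footnote to Figure 1 refer sampling details to Appendix B and to a laboratory manual.

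**The concern.** Read with a calculator, the paragraph cannot be carried out at its own lower limit: the three weighed portions need more than the smallest stated biopsy before anything goes into RNA-later. If staff filled the portions in the order listed, a 500 mg biopsy would be used up by the frozen and single-cell portions.

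The formalin portion provides Ki67, and so CCCA and PEPI-0 (a secondary objective, at day 21 and surgery). It also provides the immunohistochemistry named for the primary endpoint and the tumour check. If short samples came mainly from tumours that had shrunk, the missing readings would depend on response. The CCCA rate and the immune trajectory would then rest on a selected set of patients.

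**Working it through.** **Inputs**, all from Tissue samples: total T = 500 to 1000 mg; frozen 250 to 500; single-cell 250 to 500; histology 100 to 300; RNA-later m, not stated. Every mass is qualified as approximate.

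**1. Do the sums reproduce the stated total?**
- Minima: 250 + 250 + 100 = 600 mg against 500 mg. Excess 100 mg; 100/500 = 20%.
- Maxima: 500 + 500 + 300 = 1300 mg against 1000 mg. Excess 300 mg; 300/1000 = 30%.
- Portions 1 and 2 alone: 250 + 250 = 500 and 500 + 500 = 1000, exactly the stated total. The likely origin of the slip is that the total was set for these two portions and histology and RNA-later were not added.

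Reading the total as the mass of each separate portion does not help, because the histology range (100 to 300 mg) lies wholly below 500 mg.

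**2. Where do the ranges conflict?**
- A feasible split needs T to be at least the sum of the minima, 600 + m. It does not need T to reach the sum of the maxima, because an upper limit is not a requirement.
- At T = 1000 the three minima leave 1000 − 600 = 400 mg. The 30% figure is therefore not a shortfall.
- At T = 600 the three weighed minima just fit.
- For the unsized portion, assume m between 100 mg (the histology minimum) and 250 mg (the frozen minimum). All four portions then fit from 700 to 850 mg upward. Below that, at least one portion is smaller than its nominal minimum.

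**3. What happens at 500 mg?**

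| Way of dividing | Frozen | Single-cell | Histology | Left for RNA-later |
|---|---|---|---|---|
| Listed order, minima first | 250 | 250 | 0 | 0 |
| Histology first, rest to portions 1 and 2 | 200 | 200 | 100 | 0 |
| Histology first, rest in three equal parts | 133 | 133 | 100 | 133 |
| Pro rata over the weighed three (factor 500/600 = 0.833) | 208 | 208 | 83 | 0 |

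Only the first row leaves histology empty. It needs a filling rule that the protocol does not contain, and it breaks the requirement in Pathology / Histology for a formalin sample at every time point. In the second row the other two weighed portions get 200/250 = 80% of their nominal minimum.

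**4. Does a smaller portion mean a lost assay?** The laboratory appendix states inputs of about 10,000 live cells for single-cell work, 1 μg of total RNA for RNA sequencing and 1-3 μg of DNA for exome sequencing. It does not present 250 mg as an assay minimum. Its extraction section works from fresh frozen tissue and assigns no assay to the RNA-later portion, so a small or absent RNA-later portion costs no named endpoint. The documents give no yield per milligram, so sufficiency at 133 to 200 mg cannot be proved from them; neither can failure.

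**5. Is there other tissue?** At baseline, histology, ER and HER-2 status are conditions of entry. At surgery, the Treatment section refers to a final pathological report, and Tissue samples asks that the research biopsy be taken so that normal margin assessment is preserved. Only day 21 has no second source.

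**6. Is the yield likely to fall with response?** No yields by response are given. As a rough check, treat a tumour at the 3 cm large-T2 threshold as a sphere at 1 g/mL: (π/6) × 3³ = 14.1 g. The largest stated biopsy, 1 g, is about 7% of that. Tumour volume is unlikely to limit the yield at day 21, although patients who enter on nodal stage may have smaller primaries.

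**The case for a change.** The best case for a change is that words such as about do not absorb a 20% gap plus an unsized portion, that open, ultrasound-guided and vacuum biopsies are all allowed with no minimum yield, and that no priority is stated in the documents. If histology is protected, the shortage falls on the other portions, and single-cell sequencing also serves the primary endpoint. On the protocol's own figures (14% complete and 43% partial response on MRI at 24 weeks in the trial it cites), many late biopsies will come from reduced tumours, and the design relies on comparing each patient with herself over time.

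Part of this stands. The low-end masses do not add up, the fourth portion is unsized, and day 21 has no other described tissue.

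The step to biased results does not stand. A reduced portion is not a missing assay, and nothing in the documents shows that it becomes one. A patient with complete response at surgery may have little tumour left to sample, but that is true however the biopsy is divided, and correcting the masses would not alter it. Fixing an order such as formalin, then single-cell, then frozen is partly a scientific preference, because the primary endpoint names immunohistochemistry and single-cell sequencing as alternatives among several methods. The laboratory manual may already set an order; it cannot be checked here.

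**Conclusion.** The arithmetic is right and the consequence is not. The three weighed minima exceed the smallest stated biopsy by 100 mg (20%), with RNA-later on top. The conflict ends at 600 mg for the weighed portions, and at 700 to 850 mg if RNA-later is assumed to need 100 to 250 mg. The 300 mg high-end excess is not real.

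Histology is not lost at 500 mg, because a formalin sample is required at every visit and the remaining 400 mg can be shared among the other portions. No effect on the CCCA or PEPI-0 rates, or on the immune profile, can be derived from the documents. This is a clerical inconsistency in nominal masses plus a missing bench detail, and laboratory staff would resolve both in ordinary practice without changing an endpoint, an analysis or a conclusion.

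This rests on two assumptions: that staff honour the stated formalin requirement when tissue is short, and that portions somewhat below 250 mg still meet the stated assay inputs.
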